### 10.3 METHOD OF ASSIGNMENT TO TREATMENT

Patients who meet all inclusion criteria and are subsequently not excluded by the exclusion criteria will be randomized to double-blind treatment at Visit 2 (baseline) using an interactive web-response system (IWRS). Patients will be randomized in a 1:1 ratio to one of two treatment arms (placebo or BTRX-246040 QD). Randomization will be stratified by anhedonia symptom severity, as indicated by SHAPS total score  $\leq 4$  and total score  $> 4$ . The order in which the PRT and EEfRT administrations are conducted will be assigned via IWRS.

The IWRS will be used to assign bottles containing double-blind investigational product or placebo to each patient. Site personnel may be required to confirm that they have located the correct bottles by entering a confirmation number found on the package label into the IWRS prior to dispensing the bottle(s) to the patient (see [section 10.5](#)).

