##### 13.2.8.1 PRIMARY EFFICACY ANALYSIS

The primary efficacy analysis will be on the change in Investigator-administered MADRS total score from Visit 2 (baseline) to the last visit of the 8-week double-blind treatment period Visit 7 (week 8). The key comparison will be the contrast between BTRX-246040 and placebo at Visit 7 (week 8) from a mixed-model repeated measures (MMRM) analysis. The primary analysis will use the Full Analysis Set.

A repeated measures analysis refers to a restricted-maximum-likelihood- (REML-) based, MMRM analysis using all the longitudinal observations at each post-baseline visit. The model for this analysis will include the fixed class effects of treatment, investigative site, visit, and treatment-by-visit interaction, as well as the continuous, fixed covariates of baseline Investigator-administered MADRS total score. An unstructured covariance structure will be used to model the within-patient errors. If the unstructured covariance matrix results in a lack of convergence, the heterogeneous autoregressive variance-covariance structure will be used. Least-square means (LS Means) for the difference to placebo at Week 8, with corresponding 2-sided 95% confidence intervals will be presented in tabular and graphical displays.

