## 7. STATISTICAL CONSIDERATIONS

### 7.1. ADJUSTMENTS FOR COVARIATES AND FACTORS TO BE INCLUDED IN ANALYSES

The following covariates and factors are used in the analyses. For details of their inclusion in the models, see the specific analysis section.

- Baseline score (continuous variable)
- Treatment group (BTRX-246040 or placebo)
- Pooled Investigative Site
- Study visit (Weeks 1 – 8)
- Treatment-by-visit Interaction

If over parameterization means analyses cannot be performed pooling of investigative sites will be considered, if an appropriate pooling is possible, otherwise investigative site will be removed from the analysis.

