#### 15.1.3. PRIMARY ANALYSIS OF PRIMARY EFFICACY VARIABLE

The primary objective of this study is to evaluate the effects of BTRX-246040 on symptoms of depression in adult patients with Major Depressive Disorder after 8 weeks of double-blind treatment. To meet this objective the hypothesis that BTRX-246040 is superior to placebo will be tested as follows:

$$H_0: \mu_{\text{BTRX-246040}} = \mu_{\text{placebo}} \text{ VS. } H_a: \mu_{\text{BTRX-246040}} \neq \mu_{\text{placebo}}$$

Where  $\mu$  is the change from baseline in investigator-administered MADRS total score at week 8.

The primary efficacy analysis will be performed for the full analysis set (FAS).

The primary analysis will be a MMRM. A repeated measures analysis refers to a restricted-maximum-likelihood- (REML-) based, MMRM analysis using all the longitudinal observations at each post-baseline visit. The model for this analysis will include the fixed class effects of treatment, investigative site, visit, and the treatment-by-visit interaction as well as the continuous covariate of baseline investigator-administered MADRS total score. An unstructured covariance structure will be used to model the within-patient errors. If the unstructured covariance matrix results in a lack of convergence, the heterogeneous autoregressive variance-covariance structure will be used. The difference in least square means (LS Means) between BTRX-246040 and placebo at Week 8, with corresponding 2-sided 95% confidence intervals and estimated P-values will be presented.

---

Document:	C:\Users\q718413\Documents\NEP-MDD-201_SAP_v1.0_Final_06Dec2018.docx		
Author:	[name]	Version Number:	1.0
		Version Date:	06Dec2018

Template No: CS\_TP\_BS016 Revision 4  
Effective Date: 01Apr2016

Reference: CS\_WI\_BS005

Analysis Plan

---

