#### 15.1.4. SENSITIVITY ANALYSIS OF PRIMARY EFFICACY VARIABLE

The following sensitivity analyses will be conducted on the change from baseline in investigator-administered MADRS total score to ensure robustness of the primary efficacy analysis. The FAS will be used for all sensitivity analyses unless otherwise specified.

- The primary efficacy analysis will be repeated on the PPAS, CAS, and MNRAS analysis sets.
- The MMRM model used for the primary efficacy analysis will be used to analyze the change from Baseline in investigator-administered MADRS total score at each post-Baseline visit. For each visit the difference in LS Means between BTRX-246040 and placebo will be presented alongside the 2-sided 95% confidence interval and P-value.
- ANCOVA will be used to analyze the change in investigator-administered MADRS total score from baseline to week 8, with missing data imputed. The ANCOVA model will include treatment group, investigative site as fixed effects and baseline investigator-administered MADRS total score as a covariate. Only the MADRS total score will be imputed where missing, the individual component scores will not be imputed. Imputation will be performed following visit window remapping. The following two methods of data imputation will be used:
  - Multiple imputation using Rubin's rules with SAS Proc MI and MIANALYSIS.
  - Single imputation by last observation carried forward (LOCF).
- Finally, the change from baseline in the computer-administered MADRS total score will be analyzed using the same method as the primary efficacy analysis.

Forest plots of the treatment difference and confidence intervals will be created for the primary analysis and each of the efficacy analyses.

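### The primary MMRM fits one baseline-MADRS slope to all visits; if the true slope grows over time, chance baseline imbalance at Week 8 is modestly under-corrected

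*SAP*

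**What the plan says.** The outcome of the primary model is change from baseline in investigator-rated MADRS, and SAP 15.1.3 describes an "MMRM analysis using all the longitudinal observations at each post-baseline visit". The fixed effects are treatment, followed by "investigative site, visit, and the treatment-by-visit interaction as well as the continuous covariate of baseline investigator-administered MADRS total score". Protocol 13.2.8.1 gives the same model: treatment, then "investigative site, visit, and treatment-by-visit interaction, as well as the continuous, fixed covariates of baseline Investigator-administered MADRS total score". Its plural for the covariate still names only one variable, as a main effect. The only interaction in the covariate list of SAP 7.1 is "Treatment-by-visit Interaction". On the covariance, SAP 15.1.3 says: "An unstructured covariance structure will be used to model the within-patient errors". The key comparison is the Week 8 contrast.

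Two other places matter. Protocol 10.3 says "Randomization will be stratified by anhedonia symptom severity", using SHAPS, so the arms are not balanced on MADRS by design. SAP 15.1.4 adds a Week 8 analysis of covariance with multiple imputation and with LOCF: "The ANCOVA model will include treatment group, investigative site as fixed effects and baseline investigator-administered MADRS total score as a covariate".

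**The concern.** The covariate is there to remove whatever chance difference in baseline MADRS this one randomization produces. Which slope it uses at Week 8 therefore matters. If patients improve roughly in proportion to where they start, the slope of change on baseline is minus the fraction improved, and it steepens as improvement accumulates. The trial's own response definition (a halving of the baseline score) is proportional in this sense, which makes growth plausible but does not establish it.

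With an unstructured covariance, likelihood estimation gives the less variable visits more say in the common slope. Early visits could be the less variable ones: everyone enters at MADRS 26 or above and then diverges. A slope learned largely from Weeks 1 and 2 would then be applied at Week 8. At stake are some avoidable variance and an error tied to the realized imbalance, in the primary contrast and in every endpoint that SAP 15.2.3 and 15.3.3 analyze by the primary method.

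**Working it through.** **The plan's own figure.** Protocol 13.1: 44 per arm, effect size 0.5, two-sided alpha 0.10. The noncentral t calculation gives 75.2% (normal approximation 75.8%), so the stated 75% reproduces. Going from 50 to 44 per arm implies 6/50 = 12% loss.

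**Formula.** Let b_v be the true slope of change on baseline at visit v, and S the residual covariance given baseline. With free treatment-by-visit means and complete data, the common slope tends to

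beta = w'b, with w = S⁻¹1 / (1'S⁻¹1).

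Given an observed imbalance d (active minus placebo mean baseline), the Week 8 contrast has expectation delta_8 + (b_8 − beta)d. The uncorrected share of the Week 8 adjustment is (b_8 − beta)/b_8.

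**Inputs.** Visits and model come from the documents. Slopes, SDs and correlations are assumptions, because neither document gives them.

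**Worked case, rising variance.** Slopes −0.10, −0.18, −0.30, −0.40, −0.50; residual SDs 5, 6.5, 8, 9, 10; correlation 0.8 per visit step.
- Weights: 1.047, −0.081, −0.059, 0.017, 0.076. Weeks 1 and 2 together carry 0.97.
- beta = −0.117. Gap at Week 8 = 0.500 − 0.117 = 0.383 per point of imbalance, a share of 77%.

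**Same slopes, equal SDs of 9.**
- Weights: 0.385, 0.077, 0.077, 0.077, 0.385.
- beta = −0.298. Gap = 0.202, a share of 40%.

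**Rising SDs, half the growth.** Slopes −0.30, −0.34, −0.40, −0.45, −0.50. The weights sum to 1, so the gap scales with the growth: 0.383 / 2 = 0.192, a share of 38%. Rising variance without steep growth is therefore not enough to lose most of the adjustment.

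**Wider grids (assumed inputs).**

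| Residual SD | Scenarios | Weight on Weeks 1+2 | Weight on Week 8 | Uncorrected share | Above 50% |
|---|---|---|---|---|---|
| Rising | 48 | 58% to 117% | −12% to 24% | 36% to 101% (median 67%) | 42 |
| Equal | 16 | 40% to 46% | 20% to 43% | 28% to 48% (median 42%) | 0 |

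A separate set of scenarios gave 24% to 88% with rising variance and 20% to 41% with equal variance. A flat slope gives 0%.

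**Size in MADRS points.** With an assumed baseline SD of 4.5, the SD of chance imbalance is 4.5 × √(2/50) = 0.9 points. Over the grid, a 1-SD imbalance leaves 0.12 to 0.44 points. The Week 8 standard error is about 9 × √(2/44) = 1.92 to 10 × √(2/44) = 2.13. The residue is thus 0.12/1.92 = 6% to 0.44/2.13 = 21% of one SE, or at most about 0.21² = 4% in variance. A steeper pattern (−0.15 to −0.80) left up to 0.66 per point in simulation, so 0.66 × 0.9 = 0.59 points. Variance inflation across the simulations reached 7%.

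**Simulation of the first worked case** (unstructured covariance, 50 per arm, 12% dropout, no site term, 1,500 trials per effect size):

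| | Without interaction | With interaction |
|---|---|---|
| Baseline slope applied at Week 8 (null) | −0.112 | −0.499 |
| Residual dependence per point of imbalance (null) | −0.328 | 0.054 |
| SD of Week 8 contrast (null) | 2.119 | 2.109 |
| Rejection under the null at 0.10 | 9.5% | 9.8% |
| Power for a 5-point difference | 76.3% | 77.4% |

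The change in residual dependence, 0.328 + 0.054 = 0.382, matches the analytic 0.383. The 0.054 is within simulation error, about 2.1 / (0.9 × √1500) = 0.06.

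**Cost of the term.** With a constant slope, simulation gave a variance ratio of 0.998 to 1.000. With an assumed 12-site term in the model, the cost was about 1% with a flat slope, and the gain 0 to 6% with a growing one.

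**The case against.** The two documents agree, the model is prespecified, and baseline is adjusted for. The Week 8 estimate is unbiased over randomization, and the error exists only conditional on the imbalance that occurs. Growth of the slope is nowhere documented. Regression to the mean, which Protocol 7.2 itself mentions, would put a negative slope into every visit from Week 1 and so reduce relative growth. The gain in the simulated case is about one power point. The Week 8 analysis of covariance in SAP 15.1.4 has its own Week 8 slope and appears in the planned forest plots, so a material divergence could be seen.

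Most of this stands and limits the size of the point. The analysis of covariance does not remove it: it is a sensitivity analysis on imputed data, and a difference from the MMRM would mix missing-data handling with covariate adjustment.

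Three stronger readings are tempting and not supported:
- *A growing slope alone means that Week 8 is adjusted mainly with the early-visit slope and most imbalance stays.* This also needs steep growth and rising residual variance. With equal variances, less than half stayed in every scenario examined.
- *The primary test is biased or the 75% power claim is wrong.* Type I error stays near 10%, and the power figure reproduces.
- *Every endpoint using the same method suffers equally.* By the schedule in Protocol Table 1, HADS, DARS and HAM-A have only Weeks 4 and 8 after baseline, so no early visits can dominate. Slopes and SDs interpolated to Week 4 gave about 35% to 42% uncorrected, and about 53% in the most adverse variant tried.

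**Conclusion.** The point holds as a modest refinement. One baseline slope is imposed on five visits when only the last is the key comparison. If the true slope grows, some of the correction for which the covariate was included is lost at Week 8. A 2-SD imbalance would leave twice the 1-SD figure, 0.24 to 0.88 points over the main grid, still under half a standard error. All of this rests on assumed slopes, SDs and correlations; with a constant slope nothing is lost. The case for acting is that the gain, though small, costs almost nothing if specified now, whereas choosing the term after unblinding would be post hoc.

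**What to change.** Before unblinding, add the baseline-by-visit interaction to the primary MMRM in SAP 15.1.3 and Protocol 13.2.8.1, and to the covariate list in SAP 7.1. State that the Week 8 LS-mean difference comes from that model, evaluated at the mean baseline. Carry the term into each MMRM that reuses the primary method (the per-visit and computer-administered MADRS analyses, MADRS-6, items, HADS, DARS, SHAPS, HAM-A, pain). Otherwise, justify leaving it out.

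Costs:
- Degrees of freedom: 4 for MADRS. One fewer than the post-baseline visits elsewhere gives 3 for SHAPS and pain, and 1 for HADS, DARS and HAM-A, where less benefit should be expected.
- Up to about 1% in variance if the slope is constant. The sample size does not change.
- Wording in both documents. Protocol 13.2.1 requires an amendment if a principal feature changes, so the sponsor must decide whether this is one. If only the SAP is updated, SAP 3.3, which now reports no departures from the protocol, must record the change.

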#### 15.1.4. SENSITIVITY ANALYSIS OF PRIMARY EFFICACY VARIABLE

The following sensitivity analyses will be conducted on the change from baseline in investigator-administered MADRS total score to ensure robustness of the primary efficacy analysis. The FAS will be used for all sensitivity analyses unless otherwise specified.

- The primary efficacy analysis will be repeated on the PPAS, CAS, and MNRAS analysis sets.
- The MMRM model used for the primary efficacy analysis will be used to analyze the change from Baseline in investigator-administered MADRS total score at each post-Baseline visit. For each visit the difference in LS Means between BTRX-246040 and placebo will be presented alongside the 2-sided 95% confidence interval and P-value.
- ANCOVA will be used to analyze the change in investigator-administered MADRS total score from baseline to week 8, with missing data imputed. The ANCOVA model will include treatment group, investigative site as fixed effects and baseline investigator-administered MADRS total score as a covariate. Only the MADRS total score will be imputed where missing, the individual component scores will not be imputed. Imputation will be performed following visit window remapping. The following two methods of data imputation will be used:
  - Multiple imputation using Rubin's rules with SAS Proc MI and MIANALYSIS.
  - Single imputation by last observation carried forward (LOCF).
- Finally, the change from baseline in the computer-administered MADRS total score will be analyzed using the same method as the primary efficacy analysis.

Forest plots of the treatment difference and confidence intervals will be created for the primary analysis and each of the efficacy analyses.

## 15.2. SECONDARY EFFICACY

The secondary efficacy analyses will be performed for the FAS unless otherwise specified.

### 15.2.1. SECONDARY EFFICACY VARIABLES & DERIVATIONS

#### 15.2.1.1. MADRS Total Score

The derivation of the MADRS total score is defined in [section 15.1.1](#).

#### 15.2.1.2. MADRS-6 Subscale

The MADRS-6 subscale focuses on the core symptoms of depression and is the sum of items about the following symptoms: apparent sadness, reported sadness, inner tension, lassitude, inability to feel, and pessimistic thoughts. Overall score ranges from 0 to 36.

---

Document:	C:\Users\q718413\Documents\NEP-MDD-201_SAP_v1.0_Final_06Dec2018.docx		
Author:	[name]	Version Number:	1.0
		Version Date:	06Dec2018

Template No: CS\_TP\_BS016 Revision 4  
Effective Date: 01Apr2016

Reference: CS\_WI\_BS005

Copyright © 2009, 2010, 2012, 2016 Quintiles Transnational Corp. All rights reserved.  
The contents of this document are confidential and proprietary to Quintiles Transnational Corp. Unauthorized use, disclosure or reproduction is strictly prohibited.

Analysis Plan

---

15.2.1.3. MADRS Individual Item Scores

The MADRS individual item scores refer to the 10 items, on a scale 0 – 6 which comprise the MADRS total score.

15.2.1.4. Hospital Anxiety and Depression Scale subscales

The Hospital Anxiety and Depression Scale (HADS) subscales comprises of 7 questions regarding Depression and 7 questions regarding Anxiety. Each question is rated on a scale from 0 – 3. The outcome of the HADS questionnaire is two total scores, the HADS-A (for anxiety) and the HADS-D (for depression). Both total scores are graded on a scale of 0 – 21 and can be categorized as Normal (0 – 7), Borderline Abnormal (8 – 10) and Abnormal (11 – 21). Higher scores indicate higher levels of anxiety and depression.

15.2.1.5. Dimensional Anhedonia Rating Scale

The Dimensional Anhedonia Rating Scale (DARS) is a 17-item questionnaire with each answer between 0 and 4 on a Likert scale grading (0=Not at all, 1=Slightly, 2=Moderately, 3=Mostly, 4=Very Much). Therefore, the DARS total score is on a scale of 0 – 68. The DARS Total score is broken down into four dimensions; Hobbies, Food/Drink, Social Activities and Sensory Experience.

15.2.1.6. Snaith Hamilton Pleasure Scale

The Snaith Hamilton Pleasure Scale (SHAPS) is a 14-item questionnaire. The SHAPS is scored two different ways. Under the original scoring method, each question has 4 responses, 2 of which imply agreement (Definitely Agree, Agree; each scored as 0) and 2 which imply disagreement (Disagree, Strongly Disagree; each scored as 1). Therefore, the SHAPS total score ranges 0 – 14. In this study, in addition to the traditional scoring method, an alternative scoring method will assign 1 - Strongly Agree, 2 - Agree, 3 – Disagree, and 4 – Strongly Disagree. Using this alternative scoring method, the total score ranges 14-56. In both scoring systems, higher scores indicate greater anhedonia.

15.2.1.7. Response

Response will be defined in the following three ways:

- **Clinical response** will be defined as a reduction in the investigator-administered MADRS total score of 50% between baseline and week 8.
- **Remission** will be defined as an investigator-administered MADRS total score of  $\leq 10$  at week 8.
- **Improvement** will be defined as a Clinical Global Impression Scale – Improvement (CGI-I) score of 1 or 2 at week 8. The CGI-I is a 7-point scale that relates to an improvement in patients symptoms when compared to the Clinical Global Impression Scale – Severity (CGI-S), which is also measured on a 7-point scale.

15.2.1.8. The Facial Expression Recognition Task

The FERT is a computer test used to assess attention to, and perception of, social cues and affective

---

Document:	C:\Users\q718413\Documents\NEP-MDD-201_SAP_v1.0_Final_06Dec2018.docx		
Author:	[name]	Version Number:	1.0
		Version Date:	06Dec2018

Template No: CS\_TP\_BS016 Revision 4  
Effective Date: 01Apr2016

Reference: CS\_WI\_BS005

Analysis Plan

---

information. Faces with 6 different basic emotions (happiness, fear, anger, disgust, sadness, surprise) are displayed on the screen and the patient is required to indicate the expression of the face via a button-press. Different intensity levels (10) of each emotion are presented, which increases the ambiguity of the facial expression and the sensitivity of the task (Harmer et al, 2009). In addition, neutral faces will be displayed on screen during the task and is a button-press option. Intensity levels do not apply to the neutral face but the 5 outcome measures will be reported for neutral faces as well.

There are 5 outcome measures from the FERT for each emotion. They are:

- Accuracy (%)
- Misclassification (%)
- Average reaction time (ms)
- Target sensitivity
- Response bias

These measures, along with the accuracy response for each intensity level, for each emotion will be provided by the vendor data and will be used in the analysis described in [section 15.2.3.8](#).

#### 15.2.1.9. Probabilistic Reward Task

The PRT is a measure of reward learning consisting of trials in which patients are asked to respond to two hardly distinguishable cues, of which one is more frequently rewarded. Patients complete a total 300 trials in 3 blocks of 100. Response bias for the rewarded category is the main outcome of interest (Pizzagalli, et al, 2008). In addition, the following outcome measures will be provided:

- Discriminability (subject's ability to differentiate between the two cues)
- Reaction time
- Accuracy (hit rates)

All measures will be computed and provided by the vendor in the source data for each block and as an overall total. The response bias and discriminability measures will also have log-linear adjusted values provided. The adjusted values for response bias and discriminability and original values for reaction time and hit rates at each block will be utilized in the analyses.

Additionally, there will be a series of checks on the data to insure validity of the data used in the analysis. Only subjects with data meeting the following criteria will be used in the analysis.

- The number of valid trials is >80% for each block
- Reward ratio of rich:lean is greater than 25:10 (ratio: 2.5) in each block.
- The number of rich rewards is between 24 and 30, inclusively.
- The number of lean rewards is between 7 and 10, inclusively.
- The lean accuracy in each block is greater than or equal to 40%.
- The rich accuracy in each block is greater than or equal to 40%.
- For combination of blocks e.g. Main, Total: If one block is not usable, then the combo is not usable (i.e. if block 2 is not usable, then total is not usable).

---

Document:	C:\Users\q718413\Documents\NEP-MDD-201_SAP_v1.0_Final_06Dec2018.docx		
Author:	[name]	Version Number:	1.0
		Version Date:	06Dec2018

Template No: CS\_TP\_BS016 Revision 4  
Effective Date: 01Apr2016

Reference: CS\_WI\_BS005

